7.2.4 Physical Examination

The investigator or designee (a physician or licensed practitioner) will perform standard, full physical examinations as specified in the Schedules of Assessments [[Table 1](#) and [Table 2](#)]. Height and body weight will be measured at the screening visit, and the body weight measurement will be repeated on day 1 of each cycle.

7.2.5 Electrocardiogram

A standard 12-lead ECG will be performed at the screening visit for purposes of assessing subject eligibility. ECG can be repeated during the screening period. ECG assessments will be performed and assessed locally at predose and postdose (1 to 2 hours) day 1 of each cycle, at EoT visit, and during observation periods 1 and 2. The 12-lead ECGs will be recorded in triplicate (at least 2 minutes apart per time point) and transmitted electronically for central read during the Screening and Treatment Periods, and as a single assessment (in triplicate, if deemed necessary, at least 2 minutes apart per time point) and read locally during the Observation Periods 1 and 2.

ECGs will be recorded after the subject has been in a resting, supine position for at least 5 minutes. Further details of the procedure will be separately specified in the procedural manual.

7.2.6 Imaging

Chest X-ray or computed tomography (CT) scan is to be performed at screening. A chest X-ray (or CT of chest) does not need to be repeated if performed within 2 weeks prior to start of screening.

7.2.7 Eastern Cooperative Oncology Group

The ECOG Scale [Oken et al, 1982] will be used to assess performance status [[Table 9](#)] at time points outlined in the Schedules of Assessments [[Table 1](#) and [Table 2](#)].

Table 9 ECOG Performance Status

Grade	Description
0	Fully active, able to carry on all predisease performance without restriction.
1	Restricted in physically strenuous activity, but ambulatory and able to carry out work of a light or sedentary nature, e.g., light house work, office work.
2	Ambulatory and capable of all self-care, but unable to carry out any work activities. Up and about more than 50% of waking hours.
3	Capable of only limited self-care, confined to bed or chair more than 50% of waking hours.
4	Completely disabled. Cannot carry on any self-care. Totally confined to bed or chair.
5	Dead.

ECOG: Eastern Cooperative Oncology Group

7.2.8 Multigated Acquisition Scan or Echocardiogram

A MUGA or ECHO (as per standard of care) is to be performed at screening or within 28 days prior to screening.

7.2.9 Disease Assessment

Disease assessments as per standard of care and including extramedullary leukemia assessment will be performed as specified in the Schedule of Assessments [[Table 1](#) and [Table 2](#)]. The extramedullary leukemia assessment results must be entered into the eCRF. Blood samples must be submitted to a central laboratory for analysis. Please refer to the laboratory manual for additional information.

7.3 Adverse Events and Other Safety Aspects

The definitions of an AE or SAE can be found in [[Appendix 12.4 AEs: Definitions and Procedures for Recording, Evaluating, Follow-up and Reporting](#)].

The investigator and medically qualified designee(s) are responsible for detecting, documenting and recording events that met the definition of an AE or SAE. Collection, reporting and follow-up of Special Situations and defect in IP follow the procedures for AE and SAE.

7.3.1 Time Period for Collecting Adverse Event and Serious Adverse Event Information

In order to identify any events that may be associated with study procedures and could lead to a change in the conduct of the study, the sponsor collects AEs even if the subject has not received IP. AE collection will begin from time of informed consent and continue through post-treatment period and at least 30 days after last IP dose and prior to the start of new anticancer treatment. In addition, the following will be collected regardless of the start of new anticancer therapy:

- Any IP-related SAE that is ongoing will be followed until resolved
- Any SAE that is deemed to be related to IP by the investigator

7.3.2 Method of Detecting Adverse Events and Serious Adverse Events

The methods of recording, evaluating and assessing seriousness, causality and severity of AEs and SAEs are described in [[Appendix 12.4 AEs: Definitions and Procedures for Recording, Evaluating, Follow-up or Reporting](#)]. Care will be taken not to introduce bias when detecting AEs and/or SAEs. Open-ended and nonleading verbal questioning of the subject is the preferred method to inquire about AE occurrences.

An AE with a change in severity is recorded as a new AE.

7.3.3 Follow-up of Adverse Events

If after the protocol-defined AE collection period [see Section [7.3.1 Time Period for Collecting AE and SAE Information](#)], an AE progresses to an SAE, or the investigator learns of any (S)AE (SAE or AE) including death, where he/she considers there is reasonable possibility it is related to the IP or study participation, the investigator must promptly notify

the sponsor. Such events should be collected and followed up until resolved or judged to be no longer clinically significant, or until they become chronic to the extent that they can be fully characterized by the investigator.

7.3.4 Reporting of Serious Adverse Events

Prompt notification by the investigator to the sponsor of an SAE is essential, so that legal obligations and ethical responsibilities towards the safety of subjects and the safety of a study intervention under clinical investigation are met.

In the case of an SAE, the investigator must contact the sponsor by fax or email immediately (within 24 hours of awareness).

Procedures for reporting SAEs to the sponsor are described in [Section 12.4.5 Reporting Procedures for SAEs or Defect of Investigational Product].

7.3.5 Disease-related Events and/or Disease-related Outcomes Not Qualifying as Adverse Events or Serious Adverse Events

Under this protocol, the following event(s) will not be considered as an (S)AE:

- Disease progression: events including defined study endpoints that are clearly consistent with the expected pattern of progression of the underlying disease are not to be recorded as AEs. These data will be captured as efficacy assessment data as outlined in [Section 7.1 Efficacy Assessments]. If there is any uncertainty as to whether an event is due to anticipated disease progression and/or if there is evidence suggesting a causal relationship between the IP and the event, it should be reported as an (S)AE. All deaths up to 30 days after the final administration of IP must be reported as an SAE, even if attributed to disease progression.
- Pre-planned and elective hospital/clinical procedures/interventions or procedures for diagnostic, therapeutic, or surgical procedures for a pre-existing condition that did not worsen during the course of the study. For example, admission for treatment of a pre-existing condition not associated with the development of a new AE or with a worsening of the preexisting condition such as transfusion for preexisting anemia, leukopenia or thrombocytopenia will not be reported as an SAE. These procedures are collected per the eCRF's completion guidelines.

7.3.6 Special Situations

Certain special situations observed in association with the IP, such as incorrect administration (e.g., wrong dose of IP or background therapy) are collected in the eCRF, as protocol deviation per [Section 10.3 Major Protocol Deviations] or may require special reporting, as described below. These special situations are not considered AEs, but do require to be communicated to Astellas as per the timelines defined below.

If a special situation is associated with, or results in, an AE, the AE is to be assessed separately from the special situation and captured as an AE in the eCRF. If the AE meets the definition of an SAE, the SAE is to be reported as described in [Section 12.4.5 Reporting

Procedures for SAEs or Defect of Investigational Product] and the details of the associated special situation are to be included in the clinical description on the SAE worksheet.

The special situations are:

- Pregnancy
- Medication error, overdose and use outside protocol
- Misuse/abuse
- Occupational exposure
- (Suspicion of) Transmission of infectious agent related to microbiological contamination at the site
- Suspected drug-drug interaction

Instructions and procedures for reporting special situations are provided in [Appendix 12.4.6 Reporting Procedures for Special Situations].

7.3.7 Defects of Investigational Product

Defect is defined as the product defect, which may cause generally poor conditions where the cells cause adverse reactions that affect the human body. When a defect in IP occurs, the investigator must contact the sponsor by fax or email immediately (within 24 hours of awareness). Instructions and procedures for the expedited reporting of defects are provided in [Appendix 12.4.5 Reporting Procedures for SAEs or Defect of Investigational Product].

7.3.8 Supply of New Information Affecting the Conduct of the Study

When new information becomes available that is necessary for conducting the study properly, the sponsor will inform all investigators involved in the study as well as the appropriate regulatory authorities. Investigators should inform the IRB/IEC of such information when needed.

The investigator will also inform the subjects, who will be required to sign an updated ICF in order to continue in the study.

Specific to Japan:

1. When information is obtained regarding serious and unexpected adverse drug reactions (or other) that are specified in Article 273 of the Act on Securing Quality, Efficacy and Safety of Pharmaceuticals, Medical Devices, Regenerative and Cellular Therapy Products, Gene Therapy Products, and Cosmetics, in compliance with Article 80-2 Paragraph 6 of the Pharmaceutical Affairs Law, the sponsor should inform all investigators involved in the study, head of the study site and appropriate regulatory authorities of such information. The head of the study site who receives such information will decide whether the study should be continued after hearing the opinions of the IRB. The investigator will supply the new information to the subjects, in compliance with [Appendix 12.1.5.2 Supply of New and Important Information Influencing the Subject's Consent and Revision of the Written Information].

2. In addition, when the head of the study site receives the revisions of the investigator's brochure, protocol, written information, information on the matters covering the quality of the test product, efficacy and safety, information necessary for conducting the study properly or documents to be examined by the IRB, these documents should be sent to the IRB.
3. When the sponsor receives a safety issue from any source either Japan or worldwide that requires an urgent safety measure (USM) to be implemented, then the sponsor will report that safety information to all study sites in Japan and rest of world (within 24 hours of awareness).

7.3.9 Urgent Safety Measures

An USM is an intervention that is not defined by the protocol and can be put in place with immediate effect without needing to gain prior approval by the sponsor, relevant competent authorities (CA), IRB/IEC, where applicable, in order to protect subjects from any immediate hazard to their health and/or safety. Either the investigator or the sponsor can initiate a USM. The cause of a USM can be safety-, product- or procedure-related.

7.3.10 Reporting Urgent Safety Measures

In the event of a potential USM, the investigator must contact the study physician and/or Astellas team member (within 24 hours of awareness). Full details of the potential USM are to be recorded in the subject's medical records. The sponsor may request additional information related to the event to support their evaluation.

If the event is confirmed to be a USM, the sponsor will take appropriate action to ensure the safety and welfare of the subjects. These actions may include but are not limited to a change in study procedures or study treatment, halting further enrollment in the study, or stopping the study in its entirety. The sponsor or sponsor's designee will notify the relevant CA and concerned ethics committee within the timelines required per current local regulations, and will inform the investigators, as required. When required, investigators must notify their IRB/IEC within timelines set by regional regulations.

7.4 Pharmacokinetics

Whole blood will be collected to monitor pharmacokinetics of ASP7517 cells via determination of genomic DNA in the cell by a quantitative polymerase chain reaction method. Sampling time points are as shown in the Pharmacokinetics Sample Collection Schedule-Dose Escalation Cohort and Dose Expansion Cohort [[Table 5](#)].

Refer to the laboratory manual for detailed information regarding sampling, processing, shipping and storage instructions.

7.5 Pharmacodynamics | Biomarkers

Samples for exploratory pharmacodynamics and biomarker analyses will be collected according to the Schedules of Assessments [[Table 1](#) and [Table 2](#)].

The samples described in [Sections 7.5.1 Blood Samples and 7.5.2 Bone Marrow Aspirate Samples for Biomarker Analysis] may be analyzed for other biomarkers including DNA, RNA and protein, to investigate possible associations with mechanisms of resistance or sensitivity to study treatment, dynamic changes associated with study treatment (in terms of dose, safety, tolerability and efficacy, etc.) and method development or validation of diagnostic assays related to ASP7517.

The samples may be stored at the study sponsor's facility or a contract laboratory facility for up to 15 years after study database closure, at which time the samples will be destroyed.

The procedures for the collection, handling and shipping of laboratory samples will be specified in a laboratory manual.

7.5.1 Blood Samples

Blood samples will be collected from all subjects and used for the analysis of pharmacodynamics changes related to treatment effect and potential biomarkers of response or resistance related to treatment effect as described in [Section 9.4.3.1 Analysis of Biomarkers]. Examples of these biomarkers include, but are not limited to, cytokine expression and secretion (e.g., IFN γ), WT1-specific T lymphocytes (e.g., cytotoxic T lymphocytes), immune cell populations (e.g., NKT cells, NK cells, etc.), expression levels of WT1 and mutations in AML/MDS related genes that may modify treatment effect.

7.5.2 Bone Marrow Aspirate Samples

Bone marrow aspirate samples will be collected at the time points indicated in the Schedule of Assessments [Table 1 and Table 2] (as clinically indicated). Bone marrow aspirate samples will be used for biomarker analyses as described in [Section 9.4.3.1 Analysis of Biomarkers]. Examples of biomarkers include, but are not limited to, expression of WT1 and other genes and proteins that may be related to treatment response or treatment effect.

7.6 Other Assessments

7.6.1 Sample for the Analysis of Genes Related to Pharmacogenomics

Buccal swabs for biomarker analysis will be used to genotype the human leukocyte antigen (HLA) gene complex. Knowledge of the specific HLA gene complex in each subject may help understand/explain observed differences in efficacy or treatment effect. For detailed sample collection, sample labeling and sample shipment procedures refer to the laboratory manual. All samples will be transferred to the analytical laboratory; pharmacogenomic (PGx) samples will be kept for up to 15 years, or as specified in the ICF.

7.6.2 Sample for Optional Banked Pharmacogenomic Sample Analysis

PGx research may be conducted in the future to analyze or determine genes of relevance to clinical response, pharmacokinetics and toxicity/safety. An optional 4 to 6 mL whole blood and buccal swab sample for possible banked PGx analysis will be collected as indicated in the Schedule of Assessments [Table 1 and Table 2]. Samples will be shipped to a sponsor-designated banking clinical research organization (CRO).

Details on sample collection, labeling, storage and shipment procedures will be provided in a separate laboratory manual.

See [Appendix 12.8 Pharmacogenomic Analysis with Banked Sample] for further details on the banking procedures.

7.6.3 Sample for Anti-HLA Antibody

Blood samples will be collected from all subjects and used for the analysis of anti-HLA antibody production. Sampling time points are as shown in the Schedule of Assessments [Table 1 and Table 2]. Sample processing, storage and shipment instructions will be provided in the laboratory manual.

7.6.4 Sample for Replication Competent Lentivirus

Blood samples will be collected from all subjects and used to monitor the absence of replication competent lentivirus (RCL). Sampling time points are as shown in the Schedule of Assessments [Table 4]. If there is a positive result during the first year of assessments, additional follow-up assessments may be required on an annual basis. Sample processing, storage and shipment instructions will be provided in the laboratory manual.

7.7 Total Amount of Blood

The total amount of blood for each subject will vary depending on the course of their disease, duration on treatment and local laboratory requirements. At any time during the study, if any laboratory abnormality is found for a subject, additional blood may be drawn for safety monitoring or local standard of care.

The maximum amount of blood planned to be collected within 24 hours is approximately 71 mL on C1D1.

8 DISCONTINUATION

8.1 Discontinuation of Individual Subject(s)

A discontinuation from treatment is defined as a subject who enrolled in the study and for whom study treatment is permanently discontinued for any reason.

The subject is free to withdraw from the study treatment and/or study for any reason and at any time without giving reason for doing so and without penalty or prejudice. The investigator is also free to discontinue the subject from study treatment or to terminate a subject's involvement in the study at any time if the subject's clinical condition warrants it.

8.1.1 Discontinuation Criteria from Treatment for Individual Subject(s)

The reason for discontinuation from study treatment must be documented in the subject's medical records.

A subject must discontinue study treatment for any of the following reasons:

- Subject declines further study participation (i.e., withdrawal of consent).

- Any clinical or unacceptable AE/SAE, laboratory abnormality or intercurrent illness, in the opinion of the investigator, indicates continued treatment is not in the best interest of the subject.
- Subject is noncompliant with protocol based on the investigator or medical monitor assessment.
- Subject is found to have significantly deviated from any 1 of the inclusion or exclusion criteria after enrollment (subjects having clinical benefit and no DLT may be kept in the study after discussion with the medical monitor).
- Subject not achieving remission (CRc or PR in AML or CR, BM CR or PR or HI in MDS) and the subject is no longer deriving clinical benefit, in the opinion of the investigator.
- Subject begins other anti-leukemic therapies or MDS therapies, including undergoing HSCT.
- Subject experiences disease relapse/progression.
- Investigator/subinvestigator determines that the continuation of the study treatment will be detrimental to the subject.
- Subject is lost to follow-up despite reasonable efforts by the investigator to locate the subject.
- Female subject becomes pregnant.
- Death.
- Subject develops a grade 4 DLT during cycle 1.
- Delay of > 2 weeks of a subsequent scheduled dose of ASP7517 due to ASP7517-related toxicities.

8.1.2 Discontinuation Criteria Post-Treatment for Individual Subject(s)

The reason for discontinuation from study post-treatment must be documented in the subject's medical records.

A subject must discontinue post-treatment for any of the following reasons:

- Subject declines further study participation (i.e., withdrawal of consent).
- Subject is lost to follow-up despite reasonable efforts by the investigator to locate the subject.
- Subject begins other anti-leukemic therapies or MDS therapies, including undergoing HSCT.
- Subject experiences disease relapse/progression.
- Subject is no longer deriving clinical benefit, in the opinion of the investigator.
- Female subject becomes pregnant.
- Death.

8.2 Discontinuation of Individual Subject(s) from Study

All subjects who discontinue study treatment will remain in the study and must continue to be followed for protocol-specific follow-up procedures as outlined in [Section 4.1 Study Design] and the Schedule of Assessments [[Table 1](#), [Table 2](#), [Table 3](#) and [Table 4](#)]. The only exception to this is when the subject specifically withdraws consent for any further contact with him/her or persons previously authorized by the subject to provide this information.

All subjects who discontinue study treatment are to be followed for survival every 3 months after their final visit until death or the final analysis, whichever occurs first per [Section 4.1 Study Design] and the Schedule of Assessments [[Table 1](#), [Table 2](#), [Table 3](#) and [Table 4](#)].

8.2.1 Lost to Follow-up

Every reasonable effort is to be made to contact any subject lost to follow-up during the course of the study to complete study-related assessments, record outstanding data and retrieve IP.

8.3 Discontinuation of the Study Site

If an investigator intends to discontinue participation in the study, the investigator must immediately inform the sponsor and the head of the study site.

8.4 Discontinuation of the Study

The sponsor may terminate this study prematurely, either in its entirety or at any study site, for reasonable cause provided that written notice is submitted in advance of the intended termination. Advance notice is not required if the study is stopped due to safety concerns. If the sponsor terminates the study for safety reasons, the sponsor will immediately notify the investigator and subsequently provide written instructions for study termination.

9 STATISTICAL METHODOLOGY

A statistical analysis plan (SAP) will be written to provide details of the analysis, along with specifications for tables, listings and figures to be produced. The SAP will be finalized before the database soft-lock at the latest. Changes from the planned analyses in the final SAP that impact the statistical analyses will be justified in the clinical study report (CSR).

In general, all data will be summarized by dose level and overall with descriptive statistics for continuous endpoints, and frequency and percentage for categorical endpoints, unless otherwise specified. Percentages by categories will be based on the number of subjects with no missing data (i.e., will add up to 100%). Kaplan-Meier estimates will be provided for time-to-event endpoints. Separate data displays will be produced for each phase of the study. For phase 1 dose escalation, all data will be summarized by dose level and overall, unless otherwise specified. For phase 2 dose expansion, all data will be summarized by disease group, dose level and overall, unless otherwise specified.

Baseline will be defined as the last nonmissing observation on or prior to first administration of IP, unless otherwise specified.

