- EFS is defined as the time from the date of first dose until the date of documented relapse, treatment failure or death from any cause within 30 days after the last dose of IP (whichever occurs first earliest of [relapse date, treatment failure date, death date] - first dose date + 1).
- Duration of remission for AML includes duration of CRc, duration of CR/CRh, duration of CRh, duration of CR, and duration of response (i.e., CRc + PR).
- Duration of remission for MDS includes duration of CR and duration of response (i.e., CR + BM CR + PR).

The distribution of OS, EFS and duration of remission will be estimated for each dose level using Kaplan-Meier methodology.

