## 6 STATISTICAL METHODOLOGY

### 6.1 General Considerations

For continuous variables, descriptive statistics will include the number of subjects (n), mean, standard deviation, median, minimum and maximum. When needed, the use of other percentiles (e.g., 10%, 25%, 75% and 90%) will be reported in the relevant section. In addition, for plasma concentrations and continuous PK parameters, the coefficient of variation and the geometric mean will also be calculated. Frequencies and percentages will be displayed for categorical data. Percentages by categories will be based on the number of subjects with no missing data, i.e. will add up to 100%.

Summaries based on FAS and RAS (e.g. disposition, baseline and efficacy data) will be presented by planned treatment, unless specifically stated otherwise. Safety analysis and other summaries based on SAF, PKAS or PDAS will be presented by actual dose level received. Pharmacokinetic summaries based on PKAS and pharmacodynamic summaries based on PDAS will be presented by actual dose level received. Data for the China cohort will be summarized separately, by dose level.

All data processing, summarization, and analyses will be performed using SAS® Version 9.3 or higher on Unix. Specifications for table, figure, and data listing formats can be found in the TLF specifications for this study.

Baseline is defined as the last available measurement prior to the first dose of IP. Unless otherwise specified, all summaries will be presented overall, by dose level and by phase.

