## 6.5 Analysis of Safety

All analysis of safety will be presented overall and by dose level for SAF, unless specified otherwise. Safety data for the China cohort will be summarized separately.

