### 6.5.1 Adverse Events

For the purpose of safety assessments in this study, events recorded during the pre-investigational period will be classified as Baseline Signs and Symptoms. All adverse events (AE) recorded on treatment including within 30 days from the last study treatment will be summarized.

Summaries and listings of SAEs and Serious TEAEs include SAEs upgraded by the sponsor based on review of the Sponsor's list of Always Serious terms if any upgrade was done.

The coding dictionary for this study will be MedDRA. It will be used to summarize AEs by SOC and PT. AEs will be graded using National Cancer Institute's Common Terminology Criteria for AEs (NCI-CTCAE).

An overview table will include the following details by phase, disease type, and dose level:

- Number and percentage of subjects with TEAEs
- Number and percentage of subjects with IP related TEAEs
- Number and percentage of subjects with TEAE leading to death
- Number and percentage of subjects with IP-related TEAE leading to death
- Number and percentage of subjects with serious TEAEs and Astellas upgraded serious TEAE
- Number and percentage of subjects with serious IP related TEAEs and Astellas upgraded serious IP related TEAE
- Number and percentage of subjects with TEAEs leading to permanent discontinuation of study IP
- Number and percentage of subjects with IP related TEAEs leading to permanent discontinuation of study IP

The number and percentage of subjects with TEAEs, as classified by SOC and PT will be summarized by phase and dose level. Summaries will be provided for:

- TEAEs
- IP related TEAEs
- serious TEAEs and Astellas upgraded serious TEAE
- IP related serious TEAEs and IP related Astellas upgraded serious TEAE
- TEAEs leading to permanent discontinuation of study IP
- IP related TEAEs leading to permanent discontinuation of study IP
- TEAEs leading to dose interruption
- TEAEs excluding serious adverse events that equal to or exceed a threshold of 5% in any dose level
- Frequency reported TEAEs that equal to or exceed a threshold of 5% in any dose level

The number and percentage of subjects with TEAEs, as classified by PT only, will be summarized by phase and dose level.

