AE summary tables will include subject counts as opposed to AE counts. If a subject experiences more than one episode of a particular AE, that subject will be counted only once for that event. If a subject has more than one AE that code to the same preferred term, the subject will be counted only once for that preferred term. Similarly, if a subject has more than one AE within a body system, the subject will be counted only once in that body system.

The number and percentage of subjects with TEAEs, as classified by SOC and PT will also be summarized by NCI-CTCAE severity grade and by relationship to study drug. In the subject count, if a subject has multiple TEAEs with the same SOC or PT, but with differing severity grade or relationship, then the subject will be counted only once with the worst severity grade and highest degree of relationship, however, if any of the severity grade or relationship values are missing then the subject will be counted only once with missing severity grade or relationship. The number and percentage of subjects with CTCAE grade 3 or higher TEAE and number and percentage of subjects with CTCAE grade 3 or higher IP related TEAE will be summarized by phase and dose level.

The number and percentage of subjects with TEAEs, as classified by SOC and PT will be summarized by dose level for safety analysis set.

All AEs, deaths, SAEs, withdrawals due to adverse events, and AEs for subjects will be displayed in listings.

The list of adverse events to be summarized may change during the course of the study due to ongoing pharmacovigilance.

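### Most SAP safety tables pool AML and MDS in phase 2, although the protocol's general rule is to summarise phase 2 data by disease group

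*Protocol*

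**What the plan says.** Protocol section 9 sets the general rule: "For phase 2 dose expansion, all data will be summarized by disease group, dose level and overall, unless otherwise specified".

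The SAP sets two defaults without disease type. Section 6.1: "Unless otherwise specified, all summaries will be presented overall, by dose level and by phase". Section 6.5: "All analysis of safety will be presented overall and by dose level for SAF, unless specified otherwise".

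Within SAP 6.5.1 the overview table does keep the split: "An overview table will include the following details by phase, disease type, and dose level". The detailed tables do not. For SOC and preferred term: "The number and percentage of subjects with TEAEs, as classified by SOC and PT will be summarized by phase and dose level". For severe related events: "CTCAE grade 3 or higher IP related TEAE will be summarized by phase and dose level". The infusion-reaction and immune-related tables (6.5.2), laboratory summaries (6.5.3) and vital signs (6.5.4) use phase, dose level or both. The liver table (6.5.3.1) is given overall and by dose level, with neither phase nor disease named.

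Elsewhere the SAP names disease type: disposition (6.2.1), baseline characteristics (6.2.3), primary response (6.4.1) and best response (6.4.2.1).

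The protocol's own safety subsections do not repeat the section 9 split. Section 9.5.1 refers to treatment group, and 9.5.2 and 9.5.3 to dose level and time point.

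**The concern.** AML and MDS are two populations with separate enrolment, separate response endpoints and separate futility boundaries. If the SAP is followed as written, the tables that say which toxicities occurred, how severe they were and what happened to laboratory and liver values mix the two diseases. The overview table gives counts by disease but cannot show which event belongs to which disease.

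Safety is a primary objective. A pooled percentage is a weighted average whose weights come from futility decisions on response, which have nothing to do with safety. An event concentrated in one disease is shown at a lower rate than that disease experiences. If several doses are expanded, the weights can differ between doses, and part of an apparent dose difference may then reflect disease mix.

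**Working it through.** **Inputs.** Protocol 9.4.1.3: looks at 12 and 32, maximum 52 per disease per dose. AML stops at ≤1/12 or ≤5/32 and succeeds at ≥12/52. MDS stops at ≤0/12 or ≤4/32 and succeeds at ≥10/52. Protocol 9.1: AML 15% versus 30%, MDS 12% versus 25%, power about 0.83, type I error controlled at 0.10. The documents give no adverse event rates by disease, so all event rates below are assumptions.

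**Step 1: reproduce the plan's figure.** With X1 ~ Bin(12, p), X2 and X3 ~ Bin(20, p), first- and second-look boundaries c1 and c2, and success count r:
- P(stop at 12) = P(X1 ≤ c1)
- P(stop at 32) = Σ over x > c1 of P(X1 = x) · P(X2 ≤ c2 − x)
- P(success) = P(X1 > c1, X1 + X2 > c2, X1 + X2 + X3 ≥ r)

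Exact enumeration gives AML power 0.829 and type I error 0.067, and MDS power 0.835 and type I error 0.078. The stated 0.83 is reproduced for both, and both errors are under 0.10.

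| | stop at 12 | stop at 32 | reach 52 |
|---|---|---|---|
| AML, 15% | 0.444 | 0.272 | 0.285 |
| AML, 30% | 0.085 | 0.028 | 0.887 |
| MDS, 12% | 0.216 | 0.465 | 0.320 |
| MDS, 25% | 0.032 | 0.057 | 0.912 |

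**Step 2: dilution, which needs only one dose.** Pooled rate = (rA·nA + rM·nM)/(nA + nM). Assume 30% in AML and 4% in MDS:
- 52 + 52: (0.30×52 + 0.04×52)/104 = 17.0%
- 52 AML + 12 MDS: (15.6 + 0.48)/64 = 25.1%
- 12 AML + 52 MDS: (3.6 + 2.08)/64 = 8.9%

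The same two disease rates can be displayed as anything from 8.9% to 25.1%, depending on where each disease stopped.

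**Step 3: mix between doses, which needs at least two doses.** The AML share at a dose can run from 12/64 = 18.8% to 52/64 = 81.3%. Cross the Step 1 probabilities, taking the diseases and doses as independent and the true response rates as the same at both doses. The last two columns assume a 20-point AML–MDS event gap and no dose effect. The average distortion is 20 × the mean absolute share difference. The extreme pairing is 52:12 at one dose and 12:52 at the other, with probability 2·P(AML 52)·P(MDS 12)·P(AML 12)·P(MDS 52).

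| True response rates | unequal numbers at a dose | share differs between doses | mean share difference | average distortion | P(extreme pairing) |
|---|---|---|---|---|---|
| both inefficacious | 0.69 | 0.81 | 0.206 | 4.1 points | 1.7% |
| AML inefficacious, MDS efficacious | 0.71 | 0.69 | 0.159 | 3.2 points | 0.7% |
| AML efficacious, MDS inefficacious | 0.69 | 0.69 | 0.152 | 3.0 points | 1.0% |
| both efficacious | 0.19 | 0.33 | 0.080 | 1.6 points | 0.4% |

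The extreme, with 30% in AML and 10% in MDS: (0.30×52 + 0.10×12)/64 = 26.25% against (0.30×12 + 0.10×52)/64 = 13.75%, a 12.5-point difference. If AML stops at 12 at one dose only (12:52 against 52:52), the distortion is 20 × (0.5 − 0.1875) = 6.3 points. For assumed gaps of 10 and 30 points, that case gives 3.1 and 9.4 points, and the extreme gives 6.3 and 18.8.

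**Sensitivity.** SAP 6.7 prints 6 rather than 5 for the AML look at 32. The documents need reconciling there, but that is a separate point. With 6, AML power is 0.801, and the mean share differences become 0.196, 0.146, 0.155 and 0.086, or 3.9, 2.9, 3.1 and 1.7 points. The conclusion does not change.

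**The case against.** The strongest reply is that the protocol rule carries an exception for anything specified otherwise, and that protocol 9.5.1 to 9.5.3 name treatment group, dose level and time point without disease. On that reading the SAP follows the specific sections. This stands in part: the inconsistency lies inside the protocol as well as between the protocol and the SAP. But those subsections also do not mention phase, although section 9 requires separate displays for each phase, so they read more naturally as silent than as an instruction to pool. Either way, the text needs settling.

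Other points in the plan's favour also stand. Safety summaries are descriptive, with no test between doses. The disease mix at each dose is visible in the disposition and baseline tables. Table layouts are in specifications outside these documents. ECG summaries are by cohort and dose level, with cohort undefined, so pooling is not certain there.

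A reader might infer four stronger things that the documents do not support:
- **All adverse event tables are pooled.** The overview table is split by disease type.
- **Dose comparisons are confounded as planned.** That needs at least two expanded doses and event rates that differ by disease. More than one dose is allowed, but the planned total of 122 = 18 + 104 covers one full dose level, and no disease-specific event rates are given.
- **The disease-specific safety stop is left without data.** That stop uses DLTs and drug-related fatal events. The latter are in the overview table by disease type, and DLTs are listed with narratives.
- **The survival curves pool the diseases.** Protocol 9.4.2 does say "The distribution of OS, EFS and duration of remission will be estimated for each dose level using Kaplan-Meier methodology", without disease type. But SAP 6.4.2.3 to 6.4.2.6 now give OS, EFS, duration of response and PFS in listings only, so no pooled curve is planned.

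**Conclusion.** The concern holds in a limited form. The SAP defaults and its phase 2 safety tables other than the overview omit a disease split that protocol section 9 sets as the general rule, and the protocol's own safety subsections do not restore it. The firm consequence is that pooled rates depend on the disease mix and can dilute a toxicity specific to one disease. This needs only one dose level and a difference in event rates. The 17% illustration rests on assumed rates of 30% and 4%.

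Distortion between doses is conditional on several doses being expanded and on event rates differing by disease. For an assumed 20-point gap and equal true response rates at both doses, it averages about 2 to 4 points. The 12.5-point figure is arithmetically right but belongs to a mix with a probability of 0.4% to 1.7%, and should not be read as the expected size. This is a cheap improvement to reporting. It does not affect the primary response analysis, which is already by disease.

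**What to change.** In SAP 6.1 and 6.5, set the phase 2 default to disease type and dose level, and overall, leaving phase 1 by dose level and overall. Apply it to the SOC/PT and grade tables in 6.5.1 and to 6.5.2, 6.5.3, 6.5.3.1 and 6.5.4, keeping the pooled column beside the split. Align protocol 9.5.1 to 9.5.3 with section 9. If pooling is in fact intended for some tables, name them and give the reason. No change is needed to the time-to-event sentence or to the safety stop on this account.

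Disease type is already a classifier in the disposition, baseline and overview tables, so no new data are needed. The cost is wording, more pages, and smaller cells, which will be sparse where a disease stops at 12 subjects.
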